### 4.3. Study Termination

The investigator retains the right to terminate study participation at any time, according to the terms specified in the study contract. The investigator is to notify the IRB/IEC of the study's completion or early termination in writing, send a copy of the notification to the sponsor or sponsor's designee, and retain 1 copy for the site study regulatory file.

The sponsor may terminate the study electively if required by regulatory decision. If the study is terminated prematurely, the sponsor will notify the investigators, the IRBs and IECs, and the regulatory bodies of the decision and reason for termination of the study.

#### 5. STUDY POPULATION

Deviations from eligibility criteria are not allowed because they can potentially jeopardize the scientific integrity of the study, regulatory acceptability, and/or participant safety. Therefore, adherence to the criteria as specified in the Protocol is essential. Prospective approval of Protocol deviations to recruitment and enrollment criteria, also known as Protocol waivers or exemptions, are not permitted.

#### 5.1. Inclusion Criteria

Participants are eligible to be included in the study only if all of the following criteria apply:

- 1. Ability to comprehend and willingness to sign a written ICF for the study (or by parent or legally authorized representative).
- 2. Age  $\geq$  12 years at the time of signing the ICF.
- 3. A clinical diagnosis of nonsegmental vitiligo with depigmented area including all of the following:
  - a.  $\geq 0.5$  F-VASI on the face
  - b.  $\geq$  3.0 T-VASI (body areas not including the face)
  - c. Total body vitiligo area (facial and nonfacial) not exceeding 10% BSA.
- 4. Agree to discontinue all agents used to treat vitiligo from screening through the final safety follow-up visit. Over-the-counter preparations deemed acceptable by the investigator and camouflage makeups are permitted.
- 5. Willingness to take appropriate contraceptive measures to avoid pregnancy or fathering a child for the duration of study participation with the exception of the following:
  - a. Female participants of nonchildbearing potential (ie, or surgically sterile with a hysterectomy and/or bilateral oophorectomy OR postmenopausal [≥ 12 months of amenorrhea without an alternative medical cause]).

Note: Permitted methods in preventing pregnancy (see Appendix A) should be communicated to the participants and their understanding confirmed.

#### **5.2.** Exclusion Criteria

Participants are excluded from the study if any of the following criteria apply:

- 1. No pigmented hair within any of the vitiligo areas on the face.
- 2. Other forms of vitiligo (eg, segmental) or other differential diagnosis of vitiligo or other skin depigmentation disorders (eg, piebaldism, pityriasis alba, leprosy, postinflammatory hypopigmentation, progressive macule hypomelanosis, nevus anemicus, chemical leukoderma, and tinea versicolor).
- 3. Used depigmentation treatments (eg, monobenzone) for past treatment of vitiligo or other pigmented areas.

Note: Prior use of hydroquinone is not prohibited.

- 4. Previous pruritic, urticarial, morbilliform reaction to NB-UVB phototherapy that caused discontinuation of therapy.
- 5. Received at least 36 phototherapy sessions for vitiligo within 6 months and shown little or no repigmentation in response to previous phototherapy, including NB-UVB and excimer laser.
- 6. History of thromboembolic events (eg, deep vein thrombosis, pulmonary embolism, ischemic stroke, myocardial infarction).
- 7. Concurrent conditions and history of other diseases:
  - a. Any other skin disease that, in the opinion of the investigator, would interfere with the study cream application or study assessments.
  - b. Active acute bacterial, fungal, or viral skin infection (eg, herpes simplex, herpes zoster, chicken pox) within 1 week before baseline.
  - c. Conditions at baseline that would interfere with evaluation of vitiligo.
  - d. Any serious illness or medical, physical, or psychiatric condition(s) that, in the investigator's opinion, would interfere with full participation in the study, including application of study cream and attending required study visits; pose a significant risk to the participant; or interfere with interpretation of study data. Examples include but are not limited to the following:
    - Clinically significant or uncontrolled cardiac disease, including unstable angina, acute myocardial infarction within 6 months from Day 1 of study cream application, New York Heart Association Class III or IV congestive heart failure, and arrhythmia requiring therapy or uncontrolled hypertension (blood pressure > 150/90 mmHg) unless approved by the medical monitor/sponsor.
    - Concurrent malignant disease or a history of that in the 5 years preceding the baseline visit except for adequately treated nonmetastatic malignancies.
    - Current and/or history of liver disease, including known hepatitis B or C, with hepatic or biliary abnormalities.
    - History of tuberculosis.
    - History of alcohol use disorder or drug addiction within 1 year before screening or current alcohol or drug use that, in the opinion of the investigator, will interfere with the participant's ability to comply with the application schedule and study assessments.
    - Committed to an institution by virtue of an order issued by either the judicial or the administrative authorities.
- 8. Use of any topical drugs on the vitiligo areas (eg, corticosteroids, calcineurin, and phosphodiesterase type 4 inhibitors or retinoids) within **1 week** before baseline.
- 9. Use of any of the following treatments within 4 weeks before baseline:
  - a. Melanocyte-stimulating agents (eg. afamelanotide).
  - b. Immunomodulating systemic medications (eg, corticosteroids, methotrexate, cyclosporine).

- c. Any other systemic therapies that could increase the skin sensitivity to UV/visible light or impact skin pigmentation, for example, tetracyclines, metoxypsoralens.
- d. Received live attenuated vaccine.
- 10. Use of laser or any kind of phototherapy (including tanning bed or intentional UV exposure) within **12 weeks** before baseline.
- 11. Use of any of the following treatments within **5 half-lives or 12 weeks** (whichever is longer) before baseline:
  - a. Biologic agents for the treatment of vitiligo.
  - b. Investigational or experimental therapy or procedures for vitiligo.

Note: Investigational biologics should be discussed with the sponsor to determine whether a longer period of discontinuation is required.

- 12. Previously received JAK inhibitors, systemic or topical.
- 13. Any of the following clinical laboratory values at screening:
  - a. Hemoglobin (< 10 g/dL).
  - b. Liver function tests:
    - AST or ALT  $\geq$  2 × ULN.
    - Alkaline phosphatase and/or bilirubin > 1.5 × ULN (isolated bilirubin
       > 1.5 × ULN is acceptable if bilirubin is fractionated and direct bilirubin < 35%).

  - c. Severe renal disease (with creatinine clearance < 30 mL/min) or renal disease requiring dialysis.
  - d. Clinically significant abnormal TSH or free T4 at screening as determined by the investigator.
  - e. Positive serology test results at screening for HIV antibody.
- 14. Appropriate BMI:
  - a. Adults:  $< 17 \text{ or } > 40 \text{ kg/m}^2$ .
  - Adolescents (age ≥ 12 to < 18 years): BMI-for-age in the < 5th percentile or ≥ 85th percentile range according to the CDC BMI Percentile Calculator for Child and Teen (CDC).

- 15. Pregnant or lactating, or those considering pregnancy during the period of their study participation.
- 16. In the opinion of the investigator are unable or unlikely to comply with the application schedule and study evaluations.
- 17. Known allergy or reaction to any component of the ruxolitinib formulation.
- 18. No venous access outside of the areas to be treated.
- 19. Live with anyone participating in any current Incyte-sponsored ruxolitinib cream study.
- 20. Employees of the sponsor or investigator or are otherwise dependents of them.

### **5.3.** Lifestyle Considerations

If sunscreen, makeup, or other cosmetics have been applied to the areas to be treated, participants should follow the application guidance (see Section 6.6.1).

Participants should not take baths or showers within 2 hours after study cream application.

It is recommended that swimming should not take place within 2 hours before and after the study cream application.

#### **5.4.** Screen Failures

Screen failures are defined as participants who consent to participate in the clinical study but are not subsequently enrolled in the study.

Tests with results that fail eligibility requirements may be repeated once during screening if the investigator believes that the participant would be eligible if retested. Additionally, a participant who fails screening may repeat the screening process 1 time if the investigator believes that there has been a change in eligibility status or any laboratory abnormality is inconsistent with the participant's medical history. Participants who rescreen must reconsent and be assigned a new screening number.

### 5.5. Replacement of Participants

Participants will not be replaced during the study.

#### 6. STUDY TREATMENT

### 6.1. Study Treatments Administered

Table 6 and Table 7 present the study treatment information. Participants should apply study cream only to depigmented vitiligo areas identified by the investigator at baseline up to a T-BSA (facial and nonfacial) of  $\leq 10\%$  BSA. Participants should continue to treat all depigmented vitiligo areas identified for treatment at baseline regardless of whether the area begins to improve or fully repigment.

On visit days, study cream will be applied in the clinic during the visit. Participants should remove study cream from the tube in fingertip units until all of the areas to be treated are covered by a thin film; the tube will be weighed before and after application to determine the participant's dosage. On the day of a visit, the participant should not apply the study cream at home and will apply study cream from a new kit in the clinic during the visit under direct supervision of the site staff. Participants will be instructed to document the treated areas and be advised to limit use to no more than 1 tube (60 g) per week. Application instructions will be provided by the site study staff, and the participants will record their daily applications via a diary card given to the participants during each study visit. Refer to the Study Pharmacy Manual for participant instructions for handling of study cream.

On days where there are PK or translational assessments, study cream should be applied after these procedures have occurred.

For participants who receive combination therapy, ruxolitinib cream should be applied at least 2 hours before NB-UVB phototherapy.

See Appendix B for application instructions.

At any time, if vitiligo areas become significantly more extensive than from the previous visit, the participant should contact the study site to discuss with the investigator whether additional evaluation at the clinic is required. Participants may not treat the expanded or newly identified areas with study cream. If any other skin products that are permitted under the study Protocol are used, participants should continue these unchanged during the study.

See Appendix C for COVID-19-related guidance.

**Table 6:** Study Treatment Information (Ruxolitinib Cream)

Study treatment name:	Ruxolitinib
Dosage formulation:	Cream
Mechanism of action:	JAK inhibitor
Unit strength:	1.5%
Route of administration:	Topical
Application instructions:	A thin film is applied BID to depigmented vitiligo areas.
Packaging and labeling:	Ruxolitinib cream will be provided in 60 g tubes. Each tube will be labeled as required per country requirement.
Storage:	Ambient (15°C-30°C/59°F-86°F)
Status of treatment in participating countries:	Investigational

**Table 7:** Study Treatment Information (NB-UVB)

Study treatment name:	NB-UVB (311-312 nm)
Dosage formulation:	Cleared medical device
Dosage levels:	Starting dose = 200 mJ/cm  Increase dose by 10% at each visit until mild erythema lasting < 24 hours as reported by the participant. Hold dose at 1500 mJ/cm  – this may vary or be increased over the course of treatment. Dose information will be collected in the database.
Administration instructions:	Three times a week; not on consecutive days.
Status of treatment in participating countries:	Standard of care

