#### 6.5.3. Dose Modification for NB-UVB

On subsequent treatments, the NB-UVB machine will record participant responses about pinkness/tenderness of the skin during the previous days. Table 9 shows the dose modifications that should occur based on skin reaction. These dose modifications will be programmed into the machine. If there is severe pinkness/redness or there is pain, the participant may need to have an unscheduled visit for the investigator to evaluate the participant. The participant is not to

undergo any further light treatments until it resolves, and treatment can restart at a 15% decreased dose. Once the ordered holding dose is reached, hold at that dose until evaluated by the investigator. The holding dose may be increased at that time.

If it is unclear whether a skin reaction is related to ruxolitinib cream or the NB-UVB, the investigator should consider interrupting both.

If the participant has missed NB-UVB treatments, dose adjustments for missed treatments are listed in Table 10.

Table 9: NB-UVB Dose Adjustments Based on the Skin Assessments

Responses to NB-UVB Machine Question a	Skin Assessment	Dose Adjustment
No, or < 24 hours	No erythema reported after last treatment	Increase by 10%
24 – 48 hours	Mild erythema but not painful	Hold dose constant
> 48 hours	Moderate erythema or painful	Decrease by 10%
Still red/pain	Severe, painful erythema	Wait until resolution, decrease dose by 15%

<sup>a The NB-UVB machine will provide the following question to the participant, "Were you in pain or red after your last treatment?". The participant's response will result in a hold or change to the dose as noted in the dose adjustment column.

**Table 10:** NB-UVB Dose Adjustments for Missed Treatments

Length of Time Since Previous Dose	Dose Adjustment
Up to 1 week	Maintain dose
1-2 weeks	Decrease by 25% to a minimum of 200 mJ/cm 
2-3 weeks	Decrease by 50% to a minimum of 200 mJ/cm 
3-4 weeks	Decrease by 75% to a minimum of 200 mJ/cm 
> 4 weeks	Restart at 200 mJ/cm 

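### Table 7 ends the 10% NB-UVB increases at mild erythema lasting under 24 hours, but Table 9, programmed into the home device, adds 10% for that reaction and, read literally, for equally brief pain

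*Protocol*

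**What the plan says.** Table 7 (Protocol Section 6.1) sets a starting dose of 200 mJ/cm², three sessions a week on non-consecutive days, and this escalation rule: "Increase dose by 10% at each visit until mild erythema lasting < 24 hours as reported by the participant". It also gives a holding dose of 1500 mJ/cm², which may change during treatment.

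Section 6.5.3 then gives Table 9, says that its adjustments are programmed into the machine, and adds in a footnote that the participant's answer determines the hold or change. The device question is "Were you in pain or red after your last treatment". Table 9 has four rows:

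- Response "No, or < 24 hours", labelled "No erythema reported after last treatment": increase by 10%.
- Response of 24 to 48 hours, labelled "Mild erythema but not painful": "Hold dose constant".
- Response of more than 48 hours, labelled "Moderate erythema or painful": decrease by 10%.
- Reaction still present, labelled "Severe, painful erythema": wait for resolution, then decrease by 15%.

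The text of Section 6.5.3 adds that with severe redness, or with pain, an unscheduled visit may be needed, no light is given until the reaction resolves, and treatment can restart at a dose 15% lower. It sets no minimum duration for the pain. Section 4.1 says that the machines are for home use, and Section 5.1 admits participants from age 12.

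**The concern.** The two tables assign different actions to the same reaction. In Table 7, mild erythema lasting under 24 hours is the end point of escalation. In Table 9 it is grounds for a further increase, and mild erythema leads to a hold only once it has lasted 24 to 48 hours. The first row of Table 9 also contradicts itself, because a participant who answers under 24 hours has just reported redness or pain.

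Pain raises a second question. One device question covers both symptoms, and the answers for a reaction that has ended differ only by its duration. The response alone therefore cannot separate brief redness from brief pain.

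At stake are the dosing instructions for phototherapy taken at home, partly by adolescents, in a study with safety and tolerability of the combination as a secondary objective. Site staff and monitors who work from Table 7 would take a stop to be correct after brief erythema, while the device applies an increase. They would then lack one written standard for telling correct dosing from a deviation, or for reading an erythema or burn event against the dose given.

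**Working it through.** No figure in the plan needs reproducing, so the check sets the rules side by side and sizes the next-session difference.

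**Inputs.** Table 7: +10% per step, ending at mild erythema under 24 hours. Table 9: +10%, no change, −10% and −15% for its four rows. Section 6.5.3 text: −15% after pain has resolved. Two readings are assumed: a visit in Table 7 means a treatment session, and the end of escalation means an unchanged dose at the next session.

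| Reaction after the last session | Table 7 | Table 9, by response | Table 9, by skin-assessment label | Section 6.5.3 text |
|---|---|---|---|---|
| None | +10% | +10% | +10% | not addressed |
| Mild erythema, under 24 h | no increase | +10% | no matching label in the +10% row; mild erythema is in the hold row | not addressed |
| Mild erythema, 24–48 h | duration not addressed | hold | hold | not addressed |
| Pain, resolved, under 24 h | not addressed | +10% (literal reading) | pain appears only in the −10% and −15% rows | no light until resolved, then −15% (plain reading) |

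**Erythema under 24 hours.** Let D be the last dose.

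- Table 7: next dose = 1.00 × D.
- Table 9: next dose = 1.10 × D.
- Ratio = 1.10 / 1.00 = 1.10.

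**Resolved pain under 24 hours, literal device response.** Next dose = 1.10 × D. The comparison depends on which written rule is applied instead:

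- Hold: 1.10 / 1.00 = 1.10.
- Decrease of 10%, as in the row labelled "Moderate erythema or painful": 1.10 / 0.90 = 1.22.
- Decrease of 15%, from the Section 6.5.3 text: 1.10 / 0.85 = 1.29.

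**Which rule is delivered.** The adjustments are programmed and the answer drives the dose, so Table 9 operates. Table 7 contains no reference to Table 9 and does not defer to it. Even the hold row of Table 9 is labelled as not painful, so no label in that table supports an increase after pain.

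**The case against.** The strongest reply is that only one rule ever sets the dose. Table 9 sits in the section devoted to dose modification and is programmed into the device; Table 7 is a treatment summary. This stands, and it rules out a stronger reading that a reader might infer: that participants receive two conflicting doses. The documents show one delivered rule and a treatment table and row label that fail to match it.

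The second reply is that safeguards exist: a hold at 24 to 48 hours, a reduction beyond 48 hours, a stop while the reaction persists, a holding dose, advice to consider interrupting both treatments, and site contact after burning (Section 9.10). These limit the risk. However, the duration-based ones begin at 24 hours or while the reaction is still present, so none settles the action after brief redness that has resolved. A reader might also infer that the investigator has no say over the dose. The documents do not support that: Section 6.5.3 refers to an ordered holding dose that may be raised after investigator evaluation, and to interruption.

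Third, the pain point depends on a device script that the protocol does not reproduce in full; a follow-up question or on-screen description may exist. Table 9's labels and the Section 6.5.3 text also show an intent not to escalate after pain. Both statements are fair. A narrower reading would tie that text to reactions still present, but its wording sets no such limit. On either reading nothing written supports an increase after pain, so the gap lies between the intent and the response column.

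**Conclusion.** The mismatch between Table 7 and Table 9 is plain on the page, as is the wrong label on Table 9's first row. The demonstrated size is 10% at the next session after mild erythema lasting under 24 hours. The pain point holds with moderate confidence and only as a literal reading of the response column, because the full device script is not shown.

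Two further inferences should be resisted. A reader might compound the 10% steps up to the holding dose and claim a several-fold gap. That requires an assumed session for the first erythema, and erythema that stays under 24 hours all the way up; once it lasts 24 to 48 hours Table 9 holds the dose. The documents give no erythema or pain rates to support those inputs. A reader might also conclude that the programmed rule is unsafe. The documents do not show that, and whether to hold or continue after brief erythema is a clinical choice for the sponsor.

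No effect on the primary endpoint analysis follows from this point. SAP Section 6.6 measures NB-UVB compliance by days of use, so it does not resolve the dose rule. The point should be fixed because it concerns safety instructions and the correction is inexpensive.

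**What to change.** 1. State one action for erythema lasting under 24 hours in both tables: either change Table 9 to hold, or amend Table 7 so that escalation continues.
2. Split the first row of Table 9 into separate responses for no reaction and for a reaction under 24 hours, or relabel it so that the label fits both answers.
3. Verify that the device programming matches the chosen rule.
4. State in Section 6.5.3 that any reported pain, whatever its duration, never leads to a dose increase. Implement this by instructing participants to withhold treatment and contact the site after any pain, which does not require changing a cleared device.

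The cost is protocol wording, a participant instruction and a programming check. If the sponsor chooses to hold, or once the pain rule applies, some participants will escalate slightly more slowly. No extra participants or scheduled visits are needed.

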### 6.2. Preparation, Handling, and Accountability

The investigator or designee must confirm and document that appropriate temperature conditions (ruxolitinib cream is to be stored between 15°C and 30°C [59°F-86°F]) have been maintained during transit for all study treatments received and any discrepancies are reported and resolved before use of the study cream.

Only participants enrolled in the study may receive study treatment, and only authorized site staff may supply study cream. Immediately after application of ruxolitinib cream, participants are to wash their hands thoroughly with soap and warm water (unless the area to be treated includes the hands). Refer to the Study Pharmacy Manual for participant instructions for handling of study cream.

All study cream must be stored in a secure, environmentally controlled, and monitored (manual or automated) area in accordance with the labeled storage conditions with access limited to the investigator and authorized site staff. Participants should store study cream at ambient temperature conditions.

The investigator (or designee) is responsible for study cream accountability, reconciliation, and record maintenance (ie, receipt, reconciliation, and final disposition records). Inventory and accountability records must be maintained and readily available for inspection by the study monitor and are open to inspection at any time by any applicable regulatory authorities. The investigator or designee must maintain records that document:

- Delivery of study cream to the study site.
- Inventory of study cream at the site.
- Participant use of the study cream, including tube counts from each supply dispensed.
- Return of study cream to the investigator or designee by participants.

The investigational product must be used only in accordance with the Protocol. The investigator will also maintain records adequately documenting that the participants were provided the specified study cream. These records should include dates, quantities, and any available batch or serial numbers or unique code numbers assigned to the investigational product and study participants.

Completed accountability records will be archived by the site. The investigator or designee will be expected to collect and retain all used, unused, and partially used containers of study cream until verified by the study monitor (unless otherwise agreed to by the sponsor). At the conclusion of the study, the investigator or designee will oversee shipment of any remaining study cream back to the sponsor or its designee for destruction according to institutional SOPs. If local procedures mandate on-site destruction of investigational supply, the site should (where local procedures allow) maintain the investigational supply until the study monitor inspects the accountability records in order to evaluate compliance and accuracy of accountability by the investigative site. At sites where the study cream is destroyed before monitor inspection, the monitors rely on documentation of destruction per the site SOP.

Further guidance and information for the final disposition of unused study cream are provided in the study materials provided to sites.

